5.6 Management of Infusion Reactions

Infusion reactions are noted in the presence of high tumor burden in the treatment, and as a result are more frequent in the treatment of CLL in comparison with NHL. Stem cell transplant recipients are leukopenic and are anticipated to have an even lower likelihood of infusion reactions than B cell malignancy patients.

Infusion reactions should be managed according to the grade of the reaction. For Grade 4 reactions, the infusion must be stopped and permanently discontinued. For Grade 3 reactions, the infusion should be temporarily interrupted and appropriate medication administered to treat the symptoms. For Grade 1–2 reactions, the infusion should be slowed down and symptoms treated as appropriate. Upon resolution of symptoms, infusion can be restarted, except following Grade 4 IRR, at no more than half the previous rate and, if the patient does not experience the same adverse event with the same severity, infusion rate escalation may resume at the increments and intervals as appropriate for the treatment dose.

For infusion reactions, additional doses of H₁- and H₂-blocking antihistamine agents are administered. Corticosteroids may be administered but only for Grade 3 or 4 reactions when deemed necessary by the treating physician.

5.7 Immunosuppressive Medication Tapering

Immunosuppressive medications should be tapered according to the treating physicians' discretion with careful attention to the clinical trial or treatment plan to which the participating subject is already enrolled. The date of discontinuation of all immunosuppressive medications will be recorded.

5.8 Concomitant Medication Use

- 5.8.1 Growth Factors: Growth factors to promote WBC or RBC numbers are allowed as dictated by the clinical situation. They should not be used simply to meet eligibility requirements for subsequent obinutuzumab doses.
- 5.8.2 Immunoglobulin Repletion: ASBMT guidelines for the repletion of IgG levels should be followed. Prolonged hypogammaglobulinemia is anticipated after B cell depleting therapy.

5.9 Criteria for Taking a Participant Off Protocol Therapy

The following are criteria for removing a participant from active study:

- The development of steroid-requiring cGVHD
- Malignant disease progression
- Intercurrent illness that prevents further administration of treatment
- Unacceptable adverse event(s)
- Participant demonstrates an inability or unwillingness to comply with the treatment regimen
- Participant decides to withdraw from the protocol therapy
- General or specific changes in the participant's condition render the participant unacceptable for further treatment in the judgment of the treating investigator

Participants will be removed from the protocol therapy when any of these criteria apply. The reason for removal from protocol therapy, and the date the participant was removed, must be documented in the case report form (CRF). Patients with steroid-requiring cGVHD, unacceptable AEs or intercurrent illness preventing further drug administration who come off treatment should continue to have laboratory studies and clinical assessments performed at the appropriate timepoints. Patients with malignant disease progression do not require laboratory or clinical follow-up. Alternative care options will be discussed with the participant.

An ODQ/CTRIO Treatment Ended/Off Study Form will be filled out when a participant is removed from protocol therapy. This form can be found on the ODQ/CTRIO website or obtained from the ODQ/CTRIO registration staff.

In the event of unusual or life-threatening complications, treating investigators must immediately notify the Overall PI, [name] at [contact] [name].

5.10 Duration of Follow Up

Research subjects will be followed until 2 years from the time of transplantation, or until death, whichever occurs first. Participants removed from protocol therapy for unacceptable adverse events will be followed closely until resolution or stabilization of the adverse event, and then until 2 years from the time of transplantation, or until death, whichever occurs first. Participants who withdraw consent will be followed until that time.

5.11 Criteria for Taking a Participant Off Study

Participants will be removed from study when any of the following criteria apply:

- Lost to follow-up
- Withdrawal of consent for data submission
- Death

The reason for taking a participant off study, and the date the participant was removed, must be documented in the case report form.

For Centralized Subject Registrations, the research team submits a completed Off Treatment/Off Study form to ODQ when a participant comes off study. This form can be found on the ODQ website or obtained from the ODQ registration staff.

For Decentralized Subject Registrations, the research team updates the relevant Off Treatment/Off Study information in OnCore.

6. DOSING DELAYS/DOSE MODIFICATIONS

No dose modifications are permitted.

Dose delays are permitted only within the window of administration for that specific dose (+/- 10 days). Investigators are discouraged from using exogenous colony stimulating factors purely to attain hematologic thresholds acceptable for dosing of obinutuzumab. Criteria for the administration of doses 2, 3 and 4 are found in Section 5.4.

7. ADVERSE EVENTS: LIST AND REPORTING REQUIREMENTS

Adverse event (AE) monitoring and reporting is a routine part of every clinical trial. The following list of reported and/or potential AEs (Section 7.1) and the characteristics of an observed AE (Section 7.2) will determine whether the event requires expedited reporting **in addition** to routine reporting. Safety assessments will consist of monitoring and reporting adverse events (AEs) and serious adverse events (SAEs) that are considered related to obinutuzumab per protocol, all events of death, and any study specific issue of concern.

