7.3 Expedited Adverse Event Reporting

- 7.3.1 Investigators **must** report to the Overall PI any serious adverse event (SAE) that occurs after the initial dose of study treatment, during treatment, or within 30 days of the last dose of treatment on the local institutional SAE form.
- 7.3.2 For multi-institution studies where a DF/HCC investigator is serving as the Overall Principal Investigator, each participating institution **must** abide by the reporting requirements set by the DF/HCC. This applies to any medical event equivalent to an unexpected grade 2 or 3 with a possible, probable or definite attribution, unexpected grade 4 toxicities, and grade 5 (death) regardless of study phase or attribution.

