11.2 Data Safety Monitoring

The DF/HCC Data and Safety Monitoring Board (DSMB) will review and monitor study progress, toxicity, safety and other data from this study. The board is chaired by a medical oncologist from outside of DF/HCC and has external and internal representation. Information that raises any questions about participant safety or protocol performance will be addressed by the Overall PI, statistician and study team. Should any major concerns arise, the DSMB will offer recommendations regarding whether or not to suspend the study.

The DSMB will meet twice a year to review accrual, toxicity, response and reporting information. Information to be provided to the DSMB may include: participant accrual; treatment regimen information; adverse events and serious adverse events reported by category; summary of any deaths on study; audit results; and a summary provided by the study team. Other information (e.g. scans, laboratory values) will be provided upon request.

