12.5 Interim Monitoring Plan

The study will be monitored using standard procedures and processes by an independent Data and Safety Monitoring Board (DSMB) of the Dana-Farber Harvard Cancer Center (DF/HCC).

Monitoring of key safety endpoints (relapse, grade 3 or higher treatment related toxicity, grade III-IV acute GVHD after study enrollment) will be conducted in accordance with the DF/HCC DSMB meeting. Since a concern for excess relapse exists, even though our preliminary studies do not support this, we will compare the relapse rate along with other key safety endpoints between two arms at each interim analysis. If, at any interim analysis, this difference is significant at the two-sided level of 0.05, this would trigger a consultation with the DF/HCC DSMB for additional review of early stopping. However, this will not be a formal stopping rule that would mandate automatic closure of study enrollment.

Interim analyses for efficacy will be performed every six months in conjunction with semi-annual DF/HCC DSMB meeting, beginning at the 25% information time, which is anticipated to occur approximately 1.5 years after the start of the trial. The interim results will be reported to the DF/HCC DSMB. However, these interim analyses will not have an effect in terms of stopping accrual to the study and terminate the study early in favor of alternative (superiority) or null hypothesis (futility). This is because i) due to a small sample size at the first interim analysis, stopping early for futility would result in substantially wide confidence intervals, larger Type II error, and thus leading to greater uncertainty about the magnitude of the steroid requiring cGVHD difference, ii) by the time of the second interim analysis, the study is anticipated to complete accrual, iii) even if the steroid requiring cGVHD difference is not as large as targeted, investigators are interested in learning the magnitude of the difference for further investigation, iv) stopping early for superiority would provide less safety data than planned and potential difficulty with the efficacy analysis and its interpretation.

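### The only general toxicity endpoint in the Section 12.5 between-arm safety comparison is limited to events judged treatment-related, and no all-cause grade 3 or higher comparison by arm is planned

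*Combined protocol and SAP*

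**What the plan says.** Section 7 opens by limiting safety assessment to "adverse events (AEs) and serious adverse events (SAEs) that are considered related to obinutuzumab per protocol". The same sentence adds "all events of death, and any study specific issue of concern", which carries no attribution condition.

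Section 12.5 lists the endpoints for the DSMB: "Monitoring of key safety endpoints (relapse, grade 3 or higher treatment related toxicity, grade III-IV acute GVHD after study enrollment". It then says that "we will compare the relapse rate along with other key safety endpoints between two arms at each interim analysis". A consultation with the DSMB is triggered if "this difference is significant at the two-sided level of 0.05". The section states that this is not a formal stopping rule.

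Other sections are wider:

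- Section 7.3.1 sends the Overall PI "any serious adverse event (SAE) that occurs after the initial dose of study treatment", whatever its cause.
- Section 7.3.2 and the table in 7.3.3 cover deaths and grade 4 events regardless of attribution. A footnote exempts grade 4 events that the protocol lists as expected and not needing expedited reporting.
- Section 11.2 says the DSMB may receive "adverse events and serious adverse events reported by category; summary of any deaths on study".
- Section 12.7 compares adverse hematologic events by cumulative incidence, with no attribution condition.
- Appendix D, Section 3.9, has all toxicities evaluated.

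One section is narrower. Section 7.3.4 keeps infections out of AE reporting unless the investigator finds them highly unusual for a transplant recipient or they are fatal. Yet the lead-in to the same subsection says that exempted events still go on the case report form, and infections are a secondary endpoint in Sections 12.1 and 12.7.

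**The concern.** The trial is randomized 1:1 with placebo and a blinded study team. Transplant-related events should occur about equally in both arms, so a difference between arms estimates the harm caused by the drug, and nobody has to decide the cause of any single case. Counting only events judged related puts an investigator's opinion in front of that comparison. After transplantation, a grade 3 organ toxicity has several ready explanations other than study drug, and a blinded investigator may well choose one of them. A real excess could then be thinned out before it reaches the table that prompts the DSMB consultation.

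There is also a collection problem. A non-serious grade 3 event judged unrelated falls outside the scope stated in Section 7 and needs no expedited report under Section 7.3.3, while Appendix D has all toxicities evaluated. Sites that follow different sections could record different things, and events not recorded at the time may be hard to recover later.

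**Working it through.** **Which comparisons are filtered.**

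| Item | Section | Attribution filter? | Compared by arm? |
|---|---|---|---|
| Relapse | 12.5 | No | Yes, interim |
| Grade III-IV acute GVHD | 12.5 | No | Yes, interim |
| Grade 3+ toxicity | 12.5 | Yes | Yes, interim |
| Hematologic events | 12.7 | None stated | Yes, secondary |
| Infections | 12.1, 12.7; AE reporting limited by 7.3.4 | Investigator view on how unusual | Secondary endpoint, no method stated |
| SAEs, deaths | 7.3, 11.2 | No | Reported; no test stated |
| All-cause grade 3+ AEs | none | not applicable | Not planned |

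The gap is therefore mainly non-hematologic grade 3 or higher toxicity, together with non-fatal infections that are not reported as AEs.

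**Is there a figure to reproduce?** Not for safety: the documents give no toxicity rate, sample size or power for this comparison. The primary-endpoint power does reproduce (Fisher's exact test, 38% against 21%, 100 per arm, two-sided 0.1: 80.8% against the stated 80%), but it has no bearing here.

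**Illustration.** Inputs from the documents: 200 patients allocated 1:1, so 100 per arm (Sections 12.2 and 12.3), and two-sided 0.05 (Section 12.5). Assumed inputs: background proportion of patients with a grade 3+ event c = 0.40; drug-caused excess d = 0.15; proportion of background events called related b = 0.10; proportion of drug-caused events called related s, varied. Each patient counts once.

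- All-cause rates: c = 40% on placebo and c + d = 55% on obinutuzumab.
- Related-only rates: c×b = 0.40 × 0.10 = 4% on placebo and c×b + d×s = 4% + 15% × s on obinutuzumab.

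Power is found by summing binomial probabilities over all tables in which the uncorrected chi-square test rejects.

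| Comparison | Placebo | Obinutuzumab | Power |
|---|---|---|---|
| All-cause | 40% | 55% | 58.6% |
| Related, s = 20% | 4% | 7% | 14.0% |
| Related, s = 30% | 4% | 8.5% | 25.2% |
| Related, s = 50% | 4% | 11.5% | 52.7% |
| Related, s = 55% | 4% | 12.25% | 59.3% |
| Related, s = 70% | 4% | 14.5% | 76.3% |

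The two approaches break even at about s = 55%. If only 5% of background events are called related (b = 0.05), the rates at s = 50% are 2% and 9.5%. Power is then 64.5%, so related-only is already ahead of all-cause.

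**A second set of assumptions.** With c = 0.30, d = 0.15 and a normal approximation, all-cause power (30% against 45%) is 59%. Related-only power is:

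- 12% if b = s = 20% (6% against 9%);
- 27% if b = s = 50% (15% against 22.5%);
- 43% if b = 20% and s = 50% (6% against 13.5%);
- 82% if b = 20% and s = 90% (6% against 19.5%).

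Over c from 20% to 40% and d from 10 to 20 points, all-cause power runs from 29% to 88% and related-only power from 7% to 97%.

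**Interim size.** The figures above use full enrolment. With 50 per arm, the all-cause comparison of 40% against 55% has 34.5% power.

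**The case against.** Four arguments deserve weight.

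1. **Much of safety monitoring is unfiltered.** A reader might infer from the opening of Section 7 that safety monitoring and the DSMB comparison rest only on related toxicities. The documents do not support that. Two of the three endpoints in Section 12.5, all deaths and all SAEs are free of attribution, and Section 11.2 lets the DSMB see AEs and SAEs by category. Cytopenias, an obvious candidate for being blamed on the transplant, have their own comparison in Section 12.7 and scheduled blood counts in Section 10. This stands, and it narrows the point. It does not supply an all-cause comparison: the hematologic analysis is not among the key endpoints named in Section 12.5 and omits organ toxicity, and Section 11.2 says only what the DSMB may receive.

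2. **The filter need not be biased by arm.** It is tempting to argue that infusion reactions or B-cell results reveal the arm and so make attribution arm-dependent. That is inference. Sections 12.3 and 12.4 blind the study team apart from the pharmacy and designated unblinded staff, and Section 5.6 expects fewer infusion reactions than in B-cell malignancy. The risk that the documents support is lost sensitivity.

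3. **Attribution can help.** If investigators attribute accurately, removing background noise raises power, as the working shows. This stands, and it is the reason to keep the related subset.

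4. **The consequence is limited.** The trigger leads to a consultation and not to closure. This also stands, although a missed signal would mean that the consultation is not prompted by this route.

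**Conclusion.** The point holds in a limited form. One component of the interim safety comparison, general grade 3 or higher toxicity, passes through investigator attribution, and no section plans an unfiltered version. The likely loss is in non-hematologic events put down to the transplant. Infections face a separate opinion-based filter in Section 7.3.4.

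The size cannot be settled from the documents. On assumed rates of 40% and 55%, with 10% of background events called related, related-only power runs from 14% to 76% as correct attribution of drug-caused events rises from 20% to 70%, against 59% for all-cause. Related-only is worse below about 55% correct attribution and better above it, and that threshold falls if fewer background events are called related. Nothing in the documents shows where blinded attribution in this setting would lie, so relying on the related subset alone is hard to justify when both comparisons can be shown. It would also be wrong to assume that every grade 4 event is already captured, because of the footnote in Section 7.3.3. This is an inexpensive improvement to safety detection that should be made. It does not invalidate the monitoring plan.

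**What to change.** - **Section 12.5:** compare all grade 3 or higher AEs by arm regardless of attribution, with GVHD and relapse handled separately as now. Keep the treatment-related subset as a supportive comparison.
- **Infections:** include grade 3 or higher infections in that comparison, so that the exemption in Section 7.3.4 does not filter an existing secondary endpoint.
- **Section 7:** state that grade 3 or higher AEs are recorded on the case report form regardless of attribution. Expedited reporting rules can stay as they are.
- **Reconcile** Section 7, Sections 7.3.1 to 7.3.4, Section 11.2, Section 12.5 and Appendix D Section 3.9, so that sites have one rule on what is collected and the DSMB has one on what is compared.

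The cost is additional case report form entries for grade 3 events, infections among them, and for expected grade 4 events not already reported, one extra table for each DSMB review, and short wording changes. The primary analysis and the sample size are unaffected.

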7.1 Expected Toxicities of Obinutuzumab

7.1.1 Infusion-Related Reactions

Infusion-related reactions (IRRs) were observed consistently in all obinutuzumab trials; the highest incidence of IRR was at the first infusion with the incidence decreasing rapidly with subsequent infusions. The incidence of IRR observed with combination therapy (FC and CHOP) appears similar to that observed with monotherapy. Furthermore, the incidence of IRR appears to be higher in CLL compared to NHL patients and higher in obinutuzumab- compared to rituximab-exposed patients based on evidence from studies BO21003 and BO21999. There is no clear relationship between obinutuzumab dose and the incidence of IRR based on data from study GAO4768g. In Stage 2 of the pivotal Phase III study, BO21004/CLL 11, investigating GClb vs RClb in patients with CLL, the incidence of IRR, Grade 3/4 IRR and IRR leading to discontinuation was higher in GClb arm compared to RClb. This study investigated several measures to minimize the risk of IRRs including: use of corticosteroids, withdrawal of antihypertensive treatments, slow infusion, and split dosing and the evidence suggests that these risk minimization measures decreased the risk of IRRs (all grades); however, the impact on the incidence of Grade 3-4 events and treatment discontinuations due to IRR was limited.

7.1.2 Thrombocytopenia

The main risk associated with thrombocytopenia is hemorrhage. In trial BO21004/CLL11, the overall incidence of hemorrhagic AEs was comparable between the treatment arms (8% GClb; 7% RClb) with the majority of events being of Grade 1 or 2 severity. However, and importantly, all fatal hemorrhagic events in the GClb arm occurred in Cycle 1 in contrast to such events in the RClb arm which occurred later (beyond 1 year after first administration of study drug).

7.1.3 Other AEs

Other AEs of particular interest include neutropenia, infections including progressive multifocal leukoencephalopathy (PML), and hepatitis B virus (HBV) reactivation.

7.2 Adverse Event Characteristics

• CTCAE term (AE description) and grade: The descriptions and grading scales found in the revised NCI Common Terminology Criteria for Adverse Events (CTCAE) version 4.0 will be utilized for AE reporting. All appropriate treatment areas should have access to a copy of the CTCAE version 4.0. A copy of the CTCAE version 4.0 can be downloaded from the CTEP web site http://ctep.cancer.gov/protocolDevelopment/electronic_applications/ctc.htm.

• For expedited reporting purposes only:

- AEs for the agent(s) that are listed above should be reported only if the adverse event varies in nature, intensity or frequency from the expected toxicity information which is provided.
- Other AEs for the protocol that do not require expedited reporting are outlined in the next section (Expedited Adverse Event Reporting) under the sub-heading of Protocol-Specific Expedited Adverse Event Reporting Exclusions.

• **Attribution** of the AE:

- Definite The AE *is clearly related* to the study treatment.
- Probable The AE *is likely related* to the study treatment.

- Possible The AE *may be related* to the study treatment.
- Unlikely The AE *is doubtfully related* to the study treatment.
- Unrelated The AE *is clearly NOT related* to the study treatment.

7.3 Expedited Adverse Event Reporting

- 7.3.1 Investigators **must** report to the Overall PI any serious adverse event (SAE) that occurs after the initial dose of study treatment, during treatment, or within 30 days of the last dose of treatment on the local institutional SAE form.
- 7.3.2 For multi-institution studies where a DF/HCC investigator is serving as the Overall Principal Investigator, each participating institution **must** abide by the reporting requirements set by the DF/HCC. This applies to any medical event equivalent to an unexpected grade 2 or 3 with a possible, probable or definite attribution, unexpected grade 4 toxicities, and grade 5 (death) regardless of study phase or attribution.

7.3.3 DF/HCC Expedited Reporting Guidelines

Investigative sites within DF/HCC will report AEs directly to the DFCI Office for Human Research Studies (OHRS) per the DFCI IRB reporting policy.

Other investigative sites will report AEs to their respective IRB according to the local IRB's policies and procedures in reporting adverse events. A copy of the submitted institutional AE form should be forwarded to the Overall PI within the timeframes detailed in the table below.

	DF/HCC Reportable AEs									
Attribution	Gr. 2 & 3 AE Expected	Gr. 2 & 3 AE Unexpected	Gr. 4 AE Expected	Gr. 4 AE Unexpected	Gr. 5 AE Expected or Unexpected					
Unrelated Unlikely	Not required	Not required	5 calendar days#	5 calendar days	24 hours*					
Possible Probable Definite	Not required	5 calendar days	5 calendar days#	5 calendar days	24 hours*					

[#] If listed in protocol as expected and not requiring expedited reporting, event does not need to be reported.

The Overall PI will submit AE reports from outside institutions to the DFCI OHRS according to DFCI IRB policies and procedures in reporting adverse events.

7.3.4 Protocol-Specific Expedited Adverse Event Reporting Exclusions

For this protocol only, the AEs/grades listed below do not require expedited reporting to the Overall PI or the DFCI IRB. However, they still must be reported through the routine reporting mechanism (i.e. case report form).

The appearance of signs or symptoms known to be associated with acute or chronic GVHD are specifically exempt from AE or SAE reporting, regardless of their severity.

^{*} For participants enrolled and actively participating in the study *or* for AEs occurring within 30 days of the last intervention, the AE should be reported within 1 business day of learning of the event.

Similarly, infectious complications following stem cell transplantation are common, and will not be reported as AEs unless the clinical investigator deems the infection to be very atypical for the post-transplant setting, or the infection results in death.

Relapse of the original malignancy will not be reported as an AE, but will be monitored, as detailed in section 12.7

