GI Tract Check all that apply: Esophageal web/ proximal stricture or ring Dysphagia Anorexia Nausea Vomiting Diarrhea Weight loss ≥5%* Failure to thrive Abnormality present bu	No symptoms	Symptoms without significant weight loss* (<5%)	Symptoms associated with mild to moderate weight loss* (5-15%) OR moderate diarrhea without significant interference with daily living	Symptoms associated with significant weight loss* >15%, requires nutritional supplement for most calorie needs OR esophageal dilation OR severe diarrhea with significant interference with daily living
LIVER	Normal total bilirubin and ALT or AP < 3 x ULN	Normal total bilirubin with ALT ≥3 to 5 x ULN or AP ≥ 3 x ULN	Elevated total bilirubin but ≤3 mg/dL or ALT > 5 ULN	Elevated total bilirubin > 3 mg/dL
Abnormality present bu	t explained entirely b	y non-GVHD documented	l cause (specify):	
LUNGS** Symptom score :	No symptoms	Mild symptoms (shortness of breath after climbing one flight of steps)	Moderate symptoms (shortness of breath after walking on flat ground)	Severe symptoms (shortness of breath at rest; requiring 0_2)
Lung score: % FEV1	FEV1≥80%	FEV1 60-79%	FEV1 40-59%	FEV1 ≤39%
Pulmonary function tests Not performed Abnormality present bu	t explained entirely b	y non-GVHD documented	l cause (specify):	

S	CORE 0	SCORE 1	SCORE 2	SCORE 3	
P-ROM score (see below) Shoulder (1-7): Elbow (1-7): Wrist/finger (1-7): Ankle (1-4): Abnormality present but	No symptoms	Mild tightness of arms or legs, normal or mild decreased range of motion (ROM) AND not affecting ADL by by non-GVHD documents	Tightness of arms or legs OR joint contractures, erythema thought due to fasciitis, moderate decrease ROM AND mild to moderate limitation of ADL ented cause (specify):	Contractures WITH significant decrease of ROM AND significant limitation of ADL (unable to tie shoes, button shirts, dress self etc.)	
Not examined Currently sexually active Yes No	(See Supplemental figure [‡]) females with or without discomfort on exam may have or without symptoms with symptoms with discomfort on exam Not examined Verently sexually active Yes on exam discomfort on exam				
Abnormality present but				46-4	
Other indicators, clinical score to severity (0-3) bas					
Ascites (serositis)	Myast	henia Gravis			
Pericardial Effusion	Periph	eral Neuropathy	Eosino	philia > 500/μl	
Pleural Effusion(s)	Polym	yositis	Platele	ets <100,000/µl	
Nephrotic syndrome_	Weigh	nt loss>5%* without GI	symptoms Others	(specify):	

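### Section 7.3.4 exempts GVHD-like signs and symptoms from AE and SAE reporting whatever their cause, which contradicts its own expedited-only scope

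*Combined protocol and SAP*

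**What the plan says.** Section 7.3.4 is headed as a list of exclusions from expedited reporting. Its lead-in says that the listed events "do not require expedited reporting to the Overall PI or the DFCI IRB", and adds that they must still be recorded routinely on the CRF.

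The first listed item reads: "The appearance of signs or symptoms known to be associated with acute or chronic GVHD are specifically exempt from AE or SAE reporting". It adds that this holds at any severity. The sentence asks for no GVHD diagnosis and no judgement of cause, and it makes no exception for an event attributed to study drug.

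Three other places bear on this:

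- Section 7.3.1 requires investigators to report to the Overall PI "any serious adverse event (SAE) that occurs after the initial dose of study treatment", during treatment, or up to 30 days after the last dose.
- Section 7.4.5 has a separate GVHD waiver for reporting to Genentech. It names acute and chronic GVHD themselves, so it works by diagnosis.
- Section 12.5 compares grade 3 or higher treatment-related toxicity between the arms. A difference significant at the two-sided 0.05 level triggers a DSMB consultation.

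**The concern.** A site must decide from 7.3.4 what to report, and the section gives two answers. One leaves the CRF intact and waives only the fast route. The other waives AE and SAE reporting outright.

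The choice of trigger makes this matter. Many signs associated with GVHD are not specific to it. If the sign alone is exempt, an event caused by obinutuzumab can be set aside because it resembles GVHD, before anyone has decided whether it is GVHD. At stake are prompt review by the Overall PI and the IRB and, on the literal reading, the completeness and consistency between sites of the toxicity counts that the DSMB sees. Section 12.5 follows grade III-IV acute GVHD separately, but a sign with no GVHD diagnosis would not be counted there either. It could fall between the two.

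**Working it through.** The plan gives no figure on this point, so the check sets the passages side by side.

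1. **Scope.** The heading and lead-in of 7.3.4, and the cross-reference in 7.2, point to expedited reporting only. The GVHD sentence is not so limited. The next two items point the same way as that sentence: infections (unless very atypical or fatal) and relapse are each said not to be reported as AEs. Either reading can be defended from the text.

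2. **Trigger.** Section 7.4.5 works by diagnosis and 7.3.4 by sign or symptom. Appendix F has a box for an abnormality wholly explained by something other than GVHD, but the assessment is not completed when no GVHD is documented. Section 7.3.4 has no such check.

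3. **Overlap with named drug risks.** Section 7.3.4 does not list the signs it means. The protocol's own GVHD form, Appendix F, scores ALT, alkaline phosphatase and bilirubin, with "Elevated total bilirubin > 3 mg/dL" as the highest liver score. It lists platelets below 100,000/µl among other indicators.
   - Thrombocytopenia has its own risk section, 7.1.2: "The main risk associated with thrombocytopenia is hemorrhage".
   - Section 7.1.3 names "hepatitis B virus (HBV) reactivation", which can show itself as abnormal liver tests.
   - Eligibility (3.1.9) accepts platelets from 50,000/µL. A participant without GVHD and with a count from 50,000 up to 100,000 could enter already showing an Appendix F indicator, so the sign does not identify GVHD.

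4. **What is lost, route by route.**
   - *Expedited report, thrombocytopenia.* It is listed as expected in 7.1, and the 7.3.3 table already requires nothing for expected grade 2 and 3 events. The exemption matters mainly at grade 4 (otherwise 5 calendar days, unless the protocol excludes the event) and for SAEs under 7.3.1.
   - *Expedited report, liver abnormality of unestablished cause.* Section 7.1 does not list liver injury as such, so the event would be unexpected. The table then asks for a report within 5 calendar days at grade 2 or 3 with possible or stronger attribution, and at grade 4 with any attribution. The GVHD sentence can remove both.
   - *Deaths.* Sections 7.3.2 and 7.4.1 require these whatever the attribution. The absence of a severity limit in 7.3.4 sits badly with that, but the duty stands.
   - *CRF.* Kept by the lead-in, lost on the literal sentence.
   - *Roche/Genentech.* Section 7.6 requires all SAEs and AESIs, with a copy to the Overall PI, and 7.3.4 does not touch it. For non-serious events the route is weaker: 7.5 puts thrombocytopenia and hepatitis B reactivation among events that can be considered for reporting.
   - *Scheduled data.* The calendar has blood counts at screening, at each dosing visit, about 14 days after each dose, and at months 18 and 24. It has toxicity assessments at months 3, 3.5, 6, 9, 12, 18 and 24. It has no row for liver chemistry.

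5. **Effect on 12.5.** The trial is blinded, so a literal reading would omit GVHD-like events in both arms. If some were drug-related, the observed difference would shrink and the 0.05 trigger would be less likely to be reached. Counts would also depend on how each site read 7.3.4.

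**The case against.** The strongest reply is that the section is clear in context. Its heading, its lead-in and 7.2 all confine the list to expedited reporting. A specific exclusion from the general duty in 7.3.1 is an ordinary carve-out, and 7.5 concerns Genentech, which 7.3.4 does not mention. Appendix F is a severity form, not a definition of exempt signs. Patients with evidence of hepatitis B exposure are excluded (3.2.9). A hepatitis B reactivation recognised as an infection would fall under the infection sentence rather than the GVHD one. Excusing expected GVHD manifestations from expedited reports is sensible after transplantation.

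Most of that stands, and it narrows the point. It does not remove the conflict between the lead-in and the sentence below it, nor the lack of any test of cause.

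Several stronger readings are tempting, and the documents do not support them:

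- *That GVHD-like events disappear from safety reporting, or that a site would report nothing.* The lead-in keeps the CRF. A patient hospitalised with low platelets remains an SAE reportable under 7.6.
- *That liver injury has no other source.* Toxicity visits are scheduled. Section 3.9 of Appendix D counts all laboratory tests among the safety parameters and requires life-threatening toxicities to be reported at once.
- *That infusion reactions are caught as well.* Section 7.1.1 does not describe their signs, so that overlap cannot be shown from the text.
- *That the secondary endpoint of adverse hematologic events is compromised.* Blood counts are scheduled, and nothing says that the endpoint relies on expedited reports.

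**Conclusion.** The point holds in a limited form. Section 7.3.4 contradicts itself on scope, and it exempts by appearance rather than by cause. The clearer loss is expedited reporting to the Overall PI and the IRB of non-fatal drug-related events that resemble GVHD. The further loss, of CRF entries behind the 12.5 comparison, occurs only where a site follows the literal sentence.

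No numerical size can be given. The sentence could apply to any of the 200 planned participants once dosed, because it does not depend on GVHD being present, but the documents give no rate of GVHD-like events or of misreporting. A reader might take the share of patients without chronic GVHD in DFCI 05-377 as a measure. That share counts patients, not lost events, and it ignores acute GVHD, which the exemption also covers.

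Two assumptions carry the conclusion: that sites would regard the findings on Appendix F as signs associated with GVHD, and that at least some would read the sentence as written. This is a drafting defect in safety reporting that should be corrected. It does not threaten the primary endpoint.

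**What to change.** Reword 7.3.4 to say three things:

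1. Only events that the investigator documents as caused by diagnosed acute or chronic GVHD are exempt.
2. The exemption covers expedited reporting to the Overall PI and the DFCI IRB only, and CRF recording continues.
3. Signs or symptoms with no documented GVHD diagnosis, or with a non-GVHD or possible study-drug cause, are reported as AEs or SAEs under 7.3.1 to 7.3.3.

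Align the text with the diagnosis-based waiver in 7.4.5 and with the AESI list in 7.5, and state that deaths are reported in all cases. Recording every grade 3 or higher platelet or liver abnormality whatever its cause would be an optional extra. The correction does not depend on it.

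The cost is a short amendment, a notice to sites, and some additional AE or SAE entries for events later judged to be GVHD. It needs no new tests or visits and no change in care.
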